8.9.1. Adverse Events

Verbatim descriptions of AEs will be mapped to preferred terms using the Medical Dictionary for Regulatory Activities (MedDRA). The severity of AEs will be assessed using National Cancer Institute (NCI) common toxicity criteria for adverse events (CTCAE) Version 4.0 or higher.

Drug-related AEs are those assessed by investigator as being possible, and definitely related to study drug.

Treatment-emergent adverse events (TEAEs) are defined as those events that 1) occur after the first dose of study drug, through the treatment phase, and within 30 days following the last dose of study drug or the day prior to initiation of subsequent anti-myeloma therapy, whichever occurs earlier; 2) any event with missing onset date and its resolution date is during the treatment phase; 3) any event that is considered study drug-related regardless of the start date of the event; or 4) any event that is present at baseline but worsens in severity or is subsequently considered drug-related by the investigator.

Hemorrhagic events will be identified by hemorrhage Standardized MedDRA Query [SMQ] excluding laboratory terms and will be tabulated. Major hemorrhage is a subset of hemorrhagic events which are grade ≥ 3 or serious or belong to central nervous system (CNS) hemorrhage/hematoma.

The causal relationship between the occurrence of an AE and study drug will be judged by the investigator as unrelated, possibly related, or definitely related. In the event a subject experiences repeat episodes of the same AE, then the event with the highest severity grade and/or strongest causal relationship to study drug will be used for purposes of incidence tabulations.

The analyses for AEs are summarized in Table 7. AEs will be summarized based on the number and percentage of subjects experiencing events by MedDRA system organ class and preferred term and by NCI toxicity grade.

Incidence of all reported deaths and deaths within 30 days after the last dose of study drug will be tabulated by cause of death.

8.9.1.1. Adverse Events of Special Interest

Major Hemorrhage: The PCYC standard definition of major hemorrhage is listed in Appendix 2. Major hemorrhage will be analyzed and listed.

8.9.2. Other Safety Observations

8.9.2.1. Other Malignancies

Other malignancies are defined as new malignant tumors including solid tumors, skin malignancies and hematologic malignancies and are to be reported by investigators for the duration of study treatment and during any protocol-specified follow-up periods including post-progression follow-up for overall survival. Malignancy events by preferred term and toxicity grade will be summarized for treatment emergent period and whole study period. A data listing will also be provided.

8.9.3. Laboratory Evaluation

Hematology and serum chemistry parameters will be measured at screening, on Days 1, 2, 8 and 15 of Cycle 1, and at each study visit thereafter. Urinalysis tests will be done at screening.

All laboratory values will be converted to standard international (SI) units and classified as normal, low, or high based on the Pharmacyclics standard reference ranges whenever local laboratory reference ranges are not available. The severity of laboratory abnormalities will be graded using NCI CTCAE version 4.0 or higher.

Number and percentage of subjects with treatment emergent laboratory abnormalities will be presented by treatment cohort for the following hematology and chemistry parameters: Hgb, ANC, platelets, aspartate transaminase (AST/SGOT), alanine transaminase (ALT/SGPT), albumin, total bilirubin, creatinine, estimated creatinine clearance (Clcr), lactate dehydrogenase (LDH), uric acid and electrolytes (sodium, potassium, calcium). Shift tables summarizing baseline CTCAE grade versus the worst post-baseline CTCAE grade will also be provided. The shift of creatinine clearance rate from baseline to the lowest post-baseline value will also be summarized by categories (≥ 60 , $30 - <60$, and < 30 mL/min).

To conservatively evaluate potential Drug-Induced Liver Injury (DILI), the incidence of any ALT or AST $> 3 \times$ upper limit of normal range (ULN) and any total bilirubin $> 2 \times$ ULN post baseline will be reported respectively. Subjects who had both events occurred at any time post baseline (not necessary on the same lab evaluation) plus ALP $< 2 \times$ ULN at any time post baseline will be identified as potential Hy's law cases. A full listing of ALT, AST, total bilirubin and ALP values will be provided for the potential Hy's law cases. Frequency of abnormal treatment emergent uric acid will also be summarized.

Summary statistics for hematology and chemistry parameters will be calculated by treatment cohort for the measured values and for their changes from baseline at each scheduled visit of assessment.

Graphs displaying descriptive statistics over time will be provided for selected laboratory parameters including, but not limited to, Hgb, ANC, and platelets.

Laboratory values up to 30 days after the last dose of study drug will be included in the tabulations and graphs. Laboratory values after initiation of subsequent anti-myeloma therapy will be excluded.

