### 6.5.3 Criteria for Holding or Adjusting Dexamethasone

Up to three successive dose reductions of dexamethasone, from 40 mg to 20, 8, and 4 mg per week per investigator discretion, may be instituted for related toxicity which is unmanageable by supportive measures. Failure to tolerate 4 mg per week should lead to discontinuation of drug. Specific acute toxicities commonly noted with dexamethasone and other corticosteroids include upper gastrointestinal (dyspepsia, ulcer, gastritis), neurologic (confusion, mood alteration, insomnia), edema, hyperglycemia, and muscular weakness.

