**Hematology:** Hematology parameters will be measured on Days 1, 2, 8 and 15 of Cycle 1. Thereafter, blood samples for these tests will be collected at each study visit unless otherwise indicated. Hematology parameters must include complete blood count (CBC) with differential and platelet counts. Testing will be performed at the study center's local laboratory or other clinical laboratory listed on the investigator's Form FDA 1572.

**Serum Chemistry:** Serum chemistry parameters will be measured on Days 1, 2, 8, and 15 of Cycle 1. Thereafter, blood samples for these tests will be collected at each study visit unless otherwise indicated. Chemistry parameters must include albumin, alkaline phosphatase, ALT, AST, bicarbonate, blood urea nitrogen, calcium, chloride, creatinine, glucose, lactate dehydrogenase, magnesium, phosphate, potassium, sodium, total bilirubin, total protein, and uric acid. Testing will be performed at the study center's local laboratory or other clinical laboratory listed on the investigator's Form FDA 1572.

**Pharmacokinetics:** Refer to the laboratory binder for instructions on collecting and processing these samples. All subjects regardless of cohort will have PK samples collected and processed as described in the tables below. Additional PK samples will be collected for subjects in Cohort 1 and Cohort 3 who have started dexamethasone. The actual time (versus requested time) at which each sample is drawn must be recorded using a 24-hour format. The same clock should be used for recording the time of dosing. Refer to the laboratory manual for instructions on collecting and processing these samples.

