### **8.3.5 Safety Endpoint**

Safety summaries will include tabulations in the form of tables and listings. The frequency (number and percentage) of treatment-emergent AEs will be reported by MedDRA® System Organ Class and Preferred Term. Additional AE summaries will include AE frequency by AE severity and by relationship to study drug.

Adverse events requiring permanent discontinuation of study drug will be summarized separately, both overall and by AE severity and by relationship to study drug.

The incidence of clinically significant abnormal laboratory values and vital signs will be summarized.

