	Treatment emergent worst post-baseline abnormalities	Toxicity grade+Study Period	
	Shift of toxicity grade in low direction	Toxicity grade+Study Period	
	Shift of toxicity grade in high direction	Toxicity grade+Study Period	
	Shift from baseline in Creatinine Clearance	Study Period	
	DILI related lab criteria	Study Period	
	Liver function abnormalities	DILI; NCI criteria; Hy's Law	✓, only if any potential Hy's Law identified
	Treatment emergent abnormal uric acid	Study Period	
Vital Signs			
General	Measured values and change from baseline	Visit+Study Period	
	Shift of ECOG Performance Status	Study Period	
Other Safety Observations			
General	Other malignancy	Treatment Emergent Period (primary analysis) + Study Period	✓

PT = preferred term; SOC = system organ class

Study Periods refer to Whole Study Period and Monotherapy Period

DILI = drug induced liver injury

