8.9.5. Vital Signs and Physical Examination Findings

Vital signs (blood pressure, heart rate, respiratory rate and body temperature) and weight will be recorded at screening and each study visit. Physical examination will be done at screening and symptom-directed physical examinations will be performed during the treatment period.

Summary statistics for vital signs parameters will be calculated by treatment cohort for the measured values and for their changes from baseline at each scheduled visit of assessment.

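### The SAP plans no count of subjects with abnormal vital signs, which protocol 8.3.5 promises, and leaves glucose off its list of laboratory abnormalities to be counted

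*SAP*

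**What the plan says.** **Commitment.** Protocol 8.3.5 first describes the adverse event tables and then adds a separate sentence: "The incidence of clinically significant abnormal laboratory values and vital signs will be summarized". It names no analytes and sets no thresholds. The secondary safety endpoint (protocol 4.2.2, SAP 2.2) likewise lists clinical adverse events, laboratory variables and vital signs as distinct components.

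**Data collected.** Protocol 7.1.2 requires serum chemistry on Days 1, 2, 8 and 15 of Cycle 1 and at later visits. The panel includes "creatinine, glucose, lactate dehydrogenase, magnesium, phosphate, potassium, sodium, total bilirubin, total protein, and uric acid". Vital signs, including blood pressure and heart rate, are recorded at study visits. Protocol 6.5.3 gives the common acute toxicities of dexamethasone and closes with "edema, hyperglycemia, and muscular weakness".

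**Laboratory analysis.** SAP 8.9.3 says: "Number and percentage of subjects with treatment emergent laboratory abnormalities will be presented by treatment cohort for the following hematology and chemistry parameters". A list of named parameters follows, ending in "estimated creatinine clearance (Clcr), lactate dehydrogenase (LDH), uric acid and electrolytes (sodium, potassium, calcium". The next sentence is "Shift tables summarizing baseline CTCAE grade versus the worst post-baseline CTCAE grade will also be provided". Table 7 has a chemistry row, "Shift of toxicity grade in high direction", with no analyte named.

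**Vital signs analysis.** SAP 8.9.5 says: "Summary statistics for vital signs parameters will be calculated by treatment cohort for the measured values and for their changes from baseline". The vital-signs block of Table 7 has one row for this and one for the shift in ECOG status.

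**Declared changes.** SAP section 1 says that changes to the protocol's analysis plan are documented in the SAP. Section 10 records two: the added time-to-benefit and time-to-response endpoints, and the revised definition of major hemorrhage.

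**The concern.** Incidence means a number of subjects. Means and mean changes by visit do not supply it, and a minority of subjects with markedly abnormal readings can disappear in an average. For vital signs the protocol promises a kind of result that the SAP never produces.

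Blood pressure and glucose are the two measurements that the protocol's own safety text points to. Hypertension is among the Grade 3 or 4 events above 2% in both pooled ibrutinib tables (protocol 2.4.2.1, 1071 subjects on monotherapy; 2.4.2.2, 423 subjects on combinations). Hyperglycemia is a named toxicity of dexamethasone, which Cohorts 2 and 4 take from Cycle 1 and Cohorts 1 and 3 may add after progression.

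Without counts taken from the measurements, abnormal blood pressure or glucose is counted only where an investigator judged it reportable. The study is open label (protocol 6.1), so that judgment is made knowing the treatment.

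**Working it through.** The plan gives no figure to reproduce. The check sets the sections side by side.

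1. **Vital signs.** Promised in protocol 8.3.5: incidence of clinically significant abnormal values. Planned in SAP 8.9.5 and Table 7: readings and changes from baseline. Neither place has a limit that defines abnormal or a number and percentage of subjects. No SAP output drawn from the vital-signs data meets the promise.

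2. **Declaration.** Neither of the two items in SAP section 10 concerns vital signs. By the standard the SAP sets in section 1, the difference should be recorded or removed.

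3. **Glucose in the counted list.** The protocol 7.1.2 panel has 18 analytes. Ten are on the SAP 8.9.3 list: albumin, ALT, AST, calcium, creatinine, LDH, potassium, sodium, total bilirubin and uric acid. The other 18 − 10 = 8 are not: alkaline phosphatase, bicarbonate, blood urea nitrogen, chloride, glucose, magnesium, phosphate and total protein. Of these eight, glucose is the one tied by protocol 6.5.3 to a named study-drug toxicity. Because 8.3.5 names no analytes, its absence contradicts nothing in the protocol; it is a gap in the choice of parameters.

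4. **Graded glucose elsewhere.** The shift-table sentence in 8.9.3 carries no list of its own, nor do the chemistry shift and worst-grade rows of Table 7. The natural reading is that they follow the list just before them, but the text does not say so. Graded glucose shifts are therefore neither planned by name nor expressly excluded. The by-visit chemistry statistics in 8.9.3 are unrestricted, so glucose values and changes can appear there.

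5. **What the AE tables capture.** SAP 8.9.1 and Table 7 count all TEAEs by system organ class and preferred term and by preferred term and grade, and repeat this for Grade 3 or worse. Table 7 adds dexamethasone-related TEAEs and those leading to dexamethasone reduction, withholding or discontinuation. Under protocol 9.2.1 clinically significant laboratory abnormalities are AEs. Reported hyperglycemia and hypertension are therefore counted and graded.

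6. **Who is affected.** By 31 December 2013, Stage 1 had enrolled 18 subjects in Cohort 2 and 20 in Cohort 4 (protocol 2.4.5), so 18 + 20 = 38 subjects were in cohorts with dexamethasone planned from Cycle 1. Abnormal vital signs concern all cohorts. The documents give no rate of abnormal readings without a reported AE, so the number missed cannot be calculated.

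**The case against.** The strongest reply is that the AE tables already do most of this work. The promise in 8.3.5 covers only clinically significant abnormalities, and these are what protocol 9.2.1 treats as AEs. Its definition of an AE takes in any unfavorable and unintended sign, which would include a clinically significant change in blood pressure. On that view the promise is met through TEAE tables, and asking for more is a reporting preference.

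Part of this stands. A reader might infer that hyperglycemia and hypertension will go untabulated. The documents do not support that: once reported as AEs, both appear by preferred term and grade and, for Cohorts 1 and 3, are distinguished by study period.

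A reader might also infer that leaving out glucose breaches the protocol, or that glucose is barred from every graded table. Neither follows, since 8.3.5 names no analytes and the shift-table wording has no list. Nor does the gap defeat a planned comparison of single agent with combination, because SAP 8.8 rules out inferential comparisons among cohorts.

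The reply does not settle the vital-signs point. Protocol 8.3.5 states the commitment separately from the AE tables, the endpoint names vital signs apart from clinical AEs, and the SAP never says that AE tables are meant to serve for them. On glucose, the ambiguity about shift tables is a reason to name it.

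**Conclusion.** The point holds in two parts of unequal strength. The firmer is vital signs: an incidence that the protocol promises has no counterpart in the SAP, and section 10 does not declare it. The second is glucose: not a contradiction, but an omission from the counted parameters that is hard to justify given the toxicity named in protocol 6.5.3.

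The loss is confined to measurement-based incidence for a secondary safety endpoint. The primary endpoint, the stage decisions and data collection are untouched, and events that investigators report are captured. No numerical size can be given. The glucose conclusion assumes that the graded tables follow the 8.9.3 list; if the sponsor meant shift tables to cover every gradable analyte, only the treatment-emergent count by cohort is missing for glucose, and the wording still needs to say so.

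**What to change.** - **Glucose.** Add glucose, in the high and low directions, to the SAP 8.9.3 list, and state that it enters the worst-grade and shift tables of Table 7.
- **Vital signs.** Add to SAP 8.9.5 and Table 7 the number and percentage of subjects with treatment-emergent abnormal blood pressure and heart rate, by cohort and, for Cohorts 1 and 3, by study period. The documents contain no criteria for abnormal readings, so the SAP must set them in advance, for example CTCAE-based or sponsor-standard limits used for reporting.
- **Alternative.** If vital-signs incidence is meant to come from AE tables only, record that in section 10 as a departure from protocol 8.3.5.

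The cost is SAP wording and a few extra tables from data already collected, with no added patient burden. Glucose grades need a footnote: the protocol sets no fasting requirement for chemistry draws, so some high values may reflect recent meals.

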8.9.4. Electrocardiogram

12-lead ECGs will be done at screening. ECGs will be captured on the CRFs and kept in the clinical database. No formal analysis will be performed.

8.9.5. Vital Signs and Physical Examination Findings

Vital signs (blood pressure, heart rate, respiratory rate and body temperature) and weight will be recorded at screening and each study visit. Physical examination will be done at screening and symptom-directed physical examinations will be performed during the treatment period.

Summary statistics for vital signs parameters will be calculated by treatment cohort for the measured values and for their changes from baseline at each scheduled visit of assessment.

8.9.6. ECOG Performance Status

ECOG performance status will be recorded at screening and each study visit.

A shift table will be provided for baseline score versus the maximum post-baseline score during the treatment emergent period.

9. Patient Reported Outcome

9.1. Neuropathy Assessment

The neurotoxicity (Ntx) subscale of FACT/GOG-NTX will be utilized for neuropathy assessment. The Ntx subscale scores will be derived per FACT/GOG-Ntx Scoring Guidelines⁴.

Descriptive analysis (mean, standard deviation, median, and range) will be provided by cohort for baseline subscale scores and change from baseline prior to initiation of subsequent anti-myeloma therapy. Baseline value is defined as the last score collected on or prior to first dose of study drug.

9.2. Bone Pain Assessment

Brief Pain Inventory by Cleeland² will be utilized for bone pain assessment.

Descriptive analysis (mean, standard deviation, median, and range) will be provided by cohort for baseline scores and change from baseline prior to initiation of subsequent anti-myeloma therapy. Baseline score is defined as the last score collected on or prior to first dose of study drug.

The following parameters will be summarized:

- Pain at its worst in last 24 hrs
- Pain at its least in last 24 hrs
- Pain on the average
- Pain when assessment occurred
- Pain relief in last 24 hrs
- Activity interference caused by pain in last 24 hrs
 - General activity
 - Mood
 - Walking ability
 - Normal work
 - Sleep
 - Relations with other people
 - Enjoyment of life

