### 7.1.2 Assessments During Treatment

Subjects have scheduled study visits on Days 1, 2, 8, 15, and 22 of Cycle 1. Thereafter, study visits will occur once per cycle on Day 1 ( $\pm$ 2 days) of each cycle, continuing through Cycle 12 unless otherwise indicated. After Cycle 12, study visits will occur once every 2 cycles (ie, Cycle 12, 14, 16, etc). Refer to the Schedule of Assessments ([Appendix 4](#)) for a complete list of procedures performed at each of the scheduled study visits.

**Concomitant Medications and Therapy:** Concomitant medications and therapy will be recorded at each visit; refer to [Section 6.7](#).

**Adverse Events:** The definition for an AE is provided in [Section 9.2.1](#). All medical occurrences from the time of the first administration of study drug that meet this definition must be recorded. Important additional requirements for reporting SAEs are included in [Section 9.3.3](#). Adverse events will be recorded at each visit, or as they occur during the treatment period.

**Physical Examination, Vital Signs, and Weight:** Symptom-directed PEs will be performed during the treatment period. Vital signs and weight (refer to [Section 7.1.1](#)) will be measured and recorded at each study visit unless otherwise indicated.

**ECOG Performance Status:** The ECOG will be measured and recorded at each study visit unless otherwise indicated. The ECOG index is provided in [Appendix 1](#).

**Neuropathy and Bone Pain Assessments:** Subjects will complete questionnaires for neuropathy and bone pain on Day 1 of Cycles 2, 4, 6, 8, 10, and 12. Neuropathy and bone pain assessments are not required after Cycle 12.

**Bone Marrow Aspirate and Biopsy:** A unilateral bone marrow aspirate and biopsy documenting percent marrow involvement will be repeated as necessary to document response status as clinically indicated. Analysis of bone marrow for confirmation of CR should include staining for CD138 and  $\kappa/\lambda$  mono-clonality by immunohistochemistry or immunofluorescence.

A unilateral bone marrow aspirate sample will also be collected following confirmed disease progression and can be performed any time prior to the start of a new antineoplastic treatment. Refer to [Section 4.3](#) for description of testing.

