5.7. Treatment-Emergent Period

The treatment-emergent period is defined as the period of time from the date of the first dose of study drug through 30 days after the date of the last dose of study drug (ibrutinib or dexamethasone) or the day before initiation of any subsequent anti-myeloma therapy, whichever occurs first.

The treatment-emergent period for monotherapy (Cohorts 1 and 3 only) is defined as the period of time from the date of the first dose of ibrutinib through 30 days after the date of the last dose of ibrutinib, or the day before the addition of dexamethasone, or the day before initiation of any subsequent anti-myeloma therapy, whichever occurs first.

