8.7. Subsequent Antineoplastic Therapy for Multiple Myeloma

Anti-myeloma treatments that started after discontinuation of study treatment (i.e. started after the last dose of study drug) will be considered as subsequent antineoplastic therapies for multiple myeloma. Subsequent antineoplastic therapies will be summarized by type (e.g. radiotherapy, systemic therapy, bone marrow or stem cell transplant) and preferred term.

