8.9. Safety Analyses

All safety analyses will be based on the safety population.

In Cohorts 1 and 3, subjects will be on ibrutinib monotherapy and may convert to ibrutinib and dexamethasone combination therapy at the discretion of the investigator after a confirmed PD on ibrutinib monotherapy. Thus the safety data (e.g. incidence of TEAEs, laboratory values) will be presented and distinguished as with and without dexamethasone for subjects in Cohorts 1 and 3, when applicable.

Table 7: Summary of Safety Analyses to be Performed

Category	Analysis	Summarize By	Listing
Adverse Events			
General	Overall summary	Study Period	
	TEAEs	SOC+ PT+Study Period; PT+ toxicity grade+Study Period	
	Grade 3 or worse TEAE	SOC+ PT+Study Period; PT+ toxicity grade+Study Period	
	Ibrutinib Related TEAE	SOC+ PT (Whole Study Period only)	
	Dexamethasone Related TEAE	SOC+ PT (Whole Study Period only)	
	Grade 3 or worse Ibrutinib Related TEAE	SOC+ PT (Whole Study Period only)	
	Grade 3 or worse Dexamethasone Related TEAE	SOC+ PT (Whole Study Period only)	
	TEAEs leading to treatment discontinuation		✓
	TEAEs leading to Ibrutinib discontinuation	SOC+ PT (Whole Study Period only)	
	TEAEs leading to Dexamethasone discontinuation	SOC+ PT (Whole Study Period only)	
	TEAEs leading to dose reduction or dose withheld		✓
	TEAEs leading to Ibrutinib dose reduction	SOC+ PT+Study Period	
	TEAEs leading to Dexamethasone dose reduction	SOC+ PT+Study Period	
	TEAEs leading to Ibrutinib dose withheld	SOC+ PT+Study Period	
	TEAEs leading to Dexamethasone dose withheld	SOC+ PT+Study Period	
	Serious TEAEs	SOC+ PT + Study Period; PT + toxicity grade + Study Period	✓
	Ibrutinib Related Serious TEAEs	SOC+ PT (Whole Study Period only)	
	Dexamethasone Related Serious TEAEs	SOC+ PT (Whole Study Period only)	
	Treatment emergent bleeding events	PT + toxicity grade+Study Period	

Category	Analysis	Summarize By	Listing
	Treatment emergent major hemorrhage	PT + toxicity grade+Study Period	✓
	Treatment emergent atrial fibrillation and atrial flutter events		✓
Death	Death within 30 days of last study treatment	Whole Study Period	
	All Deaths		✓
Laboratory Evaluations			
Hematology	Measured values and change from baseline	Visit+Study Period	
	Treatment emergent worst post-baseline low abnormalities	Toxicity grade+Study Period	
	Shift of toxicity grade in low direction	Toxicity grade+Study Period	
Chemistry	Measured values and change from baseline	Visit+Study Period	

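### The bone pain and neuropathy summaries for Cohorts 1 and 3 can pool scores from before and after dexamethasone is added, and no monotherapy-period version is planned

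*SAP*

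**What the plan says.** SAP 9.1 states that the neuropathy analysis is "provided by cohort for baseline subscale scores and change from baseline prior to initiation of subsequent anti-myeloma therapy". SAP 9.2 uses the same rule for bone pain: "provided by cohort for baseline scores and change from baseline prior to initiation of subsequent anti-myeloma therapy". Neither section mentions dexamethasone or the monotherapy period.

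Four other parts of the SAP fix what that rule means:

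- **8.7** defines the cut-off event: "Anti-myeloma treatments that started after discontinuation of study treatment (i.e. started after the last dose of study drug) will be considered as subsequent" therapy.
- **5.7** counts both agents as study drug, referring to "the date of the last dose of study drug (ibrutinib or dexamethasone").
- **8.3** defines a monotherapy period for Cohorts 1 and 3. It ends the day before dexamethasone is added or the day before subsequent therapy starts, whichever is earlier.
- **8.8 and 8.9** split results for these cohorts by dexamethasone use. In 8.8 the split covers six named endpoints (CBR, DCB, ORR, DOR, PFS, TTP). In 8.9 the safety data "will be presented and distinguished as with and without dexamethasone for subjects in Cohorts 1 and 3".

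Protocol 7.1.2 has subjects complete "questionnaires for neuropathy and bone pain on Day 1 of Cycles 2, 4, 6, 8, 10, and 12". Protocol 6.3.3.1 allows dexamethasone in Cohorts 1 and 3 after Cycle 1, for subjects with PD who remain clinically stable, while ibrutinib continues.

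**The concern.** SAP 1.3 describes Cohorts 1 and 3 as the cohorts that test ibrutinib alone. A table of pain change for those cohorts invites reading as a single-agent result, yet some of its scores may come from subjects who have progressed and are taking weekly dexamethasone.

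Dexamethasone could plausibly move these particular scores. Protocol 6.5.3 lists mood alteration, insomnia and muscular weakness among its common toxicities, and the SAP 9.2 interference items include mood, sleep and walking ability. Progression may move pain the other way from any steroid relief. Bone effects are also part of the stated rationale for the drug (protocol 2.3 and 2.5).

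At stake is how a descriptive result is interpreted. No hypothesis test or enrolment decision depends on it.

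**Working it through.** **Does added dexamethasone stop the Section 9 summaries?**

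1. The only cut in 9.1 and 9.2 is the start of subsequent anti-myeloma therapy.
2. Under 8.7, subsequent therapy begins after the last dose of study drug.
3. Under 5.7, dexamethasone is itself study drug, and under protocol 6.3.3.1 it is added while ibrutinib continues. It therefore starts before the last dose of study drug, not after it.
4. SAP 8.3 lists the addition of dexamethasone and the start of subsequent therapy as two separate end points. If the second covered the first, listing both would be redundant.

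The answer is no. Scores after dexamethasone is added stay in the cohort summary.

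**Does another section supply the split?**

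| Data for Cohorts 1 and 3 | Presentation without dexamethasone planned? |
|---|---|
| CBR, DCB, ORR, DOR, PFS, TTP (8.8) | Yes |
| Time to clinical benefit, time to response (8.8.3.4) | Yes |
| Adverse events and laboratory values (8.9, Table 7) | Yes, for most summaries |
| Vital signs and ECOG shift (Table 7) | Yes, by study period |
| Neuropathy and bone pain (9.1, 9.2) | No |

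**Which questionnaires can be affected?** There are six on-treatment time points: Day 1 of Cycles 2, 4, 6, 8, 10 and 12. Response evaluation begins with Cycle 2 (protocol 7.1.2). Dexamethasone may start only after Cycle 1, once PD is confirmed or repeat samples are collected (protocol 6.3.3.1). The Cycle 2 Day 1 questionnaire will therefore normally come first, which leaves 5 of the 6 open to mixing. Under protocol 4.1, subjects with PD who do not go on to dexamethasone are removed from study. On-treatment scores after confirmed PD should therefore come from dexamethasone recipients.

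**Size.** The plan states no figure for these summaries, so there is none to reproduce. At a given visit let n be the number of scores, k the number taken after dexamethasone was added, m1 the mean change in those k, and m0 the mean change in the other n − k. Then:

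- pooled mean = (1 − k/n) × m0 + (k/n) × m1
- pooled mean − m0 = (k/n) × (m1 − m0) = (k/n) × d

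The documents give neither k nor d. Protocol 2.4.5 gives Stage 1 enrolment of 13 in Cohort 1 and 18 in Cohort 3. Assuming that roughly 10% to 70% of scores at a visit follow dexamethasone:

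| n | k | Shift |
|---|---|---|
| 13 | 1 to 9 | 1/13 = 0.08d to 9/13 = 0.69d |
| 18 | 2 to 13 | 2/18 = 0.11d to 13/18 = 0.72d |

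Actual n at later visits will be smaller as subjects leave, so one subject then counts for more than 1/13 or 1/18. The sign of d is unknown: it combines progression, steroid benefit, steroid toxicity, and differences between the subjects who add dexamethasone and those who do not.

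**The case against.** **Nothing is labelled monotherapy.** A reader might infer that the SAP reports pain change after dexamethasone as the result of ibrutinib alone. The text does not support that. Section 9 says only that results are given by cohort, which amounts to a whole-course summary. SAP 8.8.1 plans a whole-course CBR for the same cohorts, so that kind of presentation is legitimate. This objection stands. What remains is that 8.8.1 sets the monotherapy result beside the whole-course one and Section 9 does not.

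**Low consequence.** Neither score is among the listed primary, secondary or exploratory endpoints. The summaries are descriptive, and SAP 8.8 rules out inferential comparison among cohorts. This stands and limits the weight of the point.

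**Few scores may be affected.** Appendix 4 of the protocol carries a note about continuing assessments until progression. If it covers the questionnaires, few or no scores after dexamethasone would exist. Its place in the table cannot be recovered from the extracted text, and protocol 7.1.2 sets no such stop, so this is unresolved. Dexamethasone also requires clinical stability and the investigator's choice.

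**The mixing need not grow with time.** A reader might infer that later visits are increasingly made up of dexamethasone recipients. The documents do not show this: subjects without progression also remain on monotherapy, and those given dexamethasone may leave sooner. Protocol 2.4.5 reports only 4 subjects treated for more than 6 cycles at the end of 2013.

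**The safety split might already apply.** The safety examples in 8.9 are an open list, so neuropathy could be argued to fall under it. But Section 9 is separate and Table 7 omits both questionnaires.

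**Extent is partly visible.** SAP 8.2.1 reports how many subjects added dexamethasone, and 8.6 reports when. That helps a reader but does not separate the scores.

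**Conclusion.** The omission is real and follows from the SAP's own definitions: for Cohorts 1 and 3, Section 9 neither cuts nor splits at the addition of dexamethasone, and no monotherapy-period version is planned. The cohort means can therefore mix two treatment periods, mainly from Cycle 4 onward.

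Size and direction cannot be determined. The pooled mean differs from the mean of scores taken before dexamethasone by (k/n) × d, with both factors unknown. It is tempting to put in numbers: 20% to 50% of scores affected and 1 to 2 points on a pain item would give 0.2 × 1 = 0.2 to 0.5 × 2 = 1.0 point. Those inputs have no basis in the documents, and d could have either sign, so the range is not a finding.

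The conclusion assumes that questionnaires continue after progression in subjects who stay on treatment, as protocol 7.1.2 implies. CBR, its interval and the Stage 2 decision are untouched. This is an inexpensive consistency repair to descriptive tables.

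**What to change.** In SAP 9.1 and 9.2, add one sentence: for Cohorts 1 and 3, change from baseline is presented for the SAP 8.3 monotherapy period, through the day before dexamethasone is added, alongside the whole-course summary already planned, which keeps its cut at subsequent therapy. Give the number of subjects contributing at each visit in both. It would also help to state whether the Appendix 4 note on assessments until progression covers the questionnaires.

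The cost is one sentence in each section and an extra table column. No new data are needed, since SAP 8.6 already derives time to addition of dexamethasone.

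There are two downsides. The monotherapy columns will hold fewer scores per visit; under 8.3 even a score taken on the day dexamethasone starts is excluded. Later monotherapy means will also come from a selected group, those who have not progressed or have not added dexamethasone, and may look better for that reason. The table note should say so, which is why both versions should be shown side by side.
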